9.2 Replacement of Subjects

Subjects who are withdrawn for personal or family reasons, who are not assessable, who dropout for medical reasons or as a consequence of exitus within 3 days of treatment will not be replaced. Each site will try to achieve the agreed number of assessable patients.

10. EMERGENCY PROCEDURES

10.1 Emergency Sponsor Contact

In emergency situations, the investigator should contact the sponsor or sponsor's representatives by telephone using the numbers listed on the title page of the protocol.

10.2 Emergency Identification of Study Medication

If it is medically imperative to know what study medication the subject is receiving, the investigator or authorized person should open the randomization envelope. The investigator or the person who breaks the blind must record the date and the reasons for doing so in the case report form, in the subject's medical record, and on the randomization envelope. In such cases, treatment with the study medication must be stopped and the sponsor's representatives contacted immediately to determine whether the subject should be withdrawn from the study. Whenever possible, the sponsor's representatives should be contacted before the blind is broken.

10.3 Emergency Treatment

During and following a subject's participation in the trial, the investigator/institution should ensure that adequate medical care is provided to a subject for any adverse events, including clinically significant laboratory values, related to the trial. The investigator/institution should inform a subject when medical care is needed for intercurrent illness(es) of which the investigator becomes aware.

11. STATISTICAL PROCEDURES

11.1 Analysis Variables

All variables collected and calculated for pharmacodynamics, pharmacokinetics and safety will be analyzed (listed under Section 7.3).

11.2 Study Populations

- All subjects who are considered as available and interpretable will be included in the clinical and pharmacodynamic analysis, providing they have completed at least 3 days of treatment prior to exitus or at least 5 days prior to extubation, and providing no major protocol violations have been identified. Cases with death occurring within 3 days of entering study and apparently triggered by other causes than *P.aeruginosa* pneumonia will not be considered as assessable
- All randomized subjects who will have received at least one dose of medication and having data considered as available and interpretable will be included in the safety analysis.

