Approximately 10-15% of the colonized patients will actually develop pneumonia, demonstrating a definite unmet medical need linked to a high risk in this ventilated population. A treatment which could control, or even inhibit, colonization of the intubation device might decrease colonization of the respiratory tract, thereby delaying the occurrence of pneumonia and allowing the patient to recover enough to be extubated prior to developing this threatening complication.

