4.2 Inclusion Criteria

Subjects meeting all of the following criteria will be considered for admission to the study:

- Male and non pregnant female aged 18 to 75 years
- Patients hospitalized in ICU, under mechanically assisted ventilation expected to be mandatory for 3 days or more
- Reasonable survival chance within next few days with an Apache score 10-25 as per Appendix H [Knaus et al 1985]
- Tracheal aspirate found positive to *P. aeruginosa*
- The subject (or a close family member in case of incompetence) understands the procedures, agrees to participate, and is willing to give his written informed consent

Informed consent must be obtained for all subjects before enrollment in the study, by patient or by close family member.

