7.1.1. Clinical efficacy data (collected at each clinical site)

Clinical efficacy (clinical site)

- Occurrence of *P. aeruginosa* pneumonia (primary variable)
The diagnosis of pneumonia will be assessed under blinded conditions by an independent panel of experts prior to stopping the study
- Occurrence of death (excluded if death within 3 days and not elicited by *P. aeruginosa*)
- Time to pneumonia, to exitus (Day -1), or to bacteremia
- Time to extubation (Day n-1)
- Overall outcome (until Day n+7)
- Duration of hospital and ICU stay
- Cost assessment
- PaO₂/ FI_{O2}
- Occurrence of infections to other bacterial strains

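### The only efficacy set, and so the primary test, depends on events after randomisation (early extubation, early death, attributed cause of death), with no all-treated analysis beside it

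*Protocol*

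**What the plan says.** Protocol Section 11.2 defines two populations.

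- **Clinical and pharmacodynamic analysis.** Patients enter "providing they have completed at least 3 days of treatment prior to exitus or at least 5 days prior to extubation". Anyone with a major protocol violation is left out. A second sentence removes early deaths by attributed cause: where the target pneumonia does not appear to be responsible, the patient "will not be considered as assessable".
- **Safety analysis.** This is the only set built from all randomised patients with at least one dose.

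Section 11.3 makes occurrence of pneumonia the primary variable, tested by Fisher's exact test (two-sided, 0.10, 10% in placebo). Section 7.1.1 lists it among the clinical efficacy variables, together with death and time to extubation, so the first population governs the primary test. In the same list the mortality variable is qualified: "excluded if death within 3 days and not elicited by" *P. aeruginosa*. When Section 11.3 speaks of all patients, it contrasts them with the antibiotic subgroups and does not define an intention-to-treat set.

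Sections 4.1 and 11.5 size the trial in assessable patients (100 to 200) and stop recruitment at 10 confirmed cases.

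**The concern.** Whether a patient is extubated before the fifth treatment day, dies before the third, or has a death attributed to one cause rather than another is known only after randomisation, and treatment may influence each. A comparison among patients selected on such events is no longer guaranteed by randomisation to compare like with like. Here the selecting events are also outcomes under test.

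The entry criteria do not prevent the problem. Section 4.2 admits patients "under mechanically assisted ventilation expected to be mandatory for 3 days or more", and Section 4.3 excludes those expected to need 3 days or less. A patient expected to need about 4 days satisfies both sections. If extubated on Day 4, which Section 7.2.5 makes the last treatment day, that patient has 4 treatment days and leaves the primary analysis.

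Section 11.2 also leaves early pneumonia unsettled. A fatal *P. aeruginosa* pneumonia before 3 treatment days fails the first sentence, while the second, which removes only deaths from other causes, implies that it stays. A non-fatal pneumonia on Day 1 or 2 ends study drug without death or extubation, so neither threshold clearly applies. Either reading moves events in a trial that plans for ten.

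**Working it through.** **1. The plan's own figures.** Section 11.5: 10 placebo cases / 0.10 = 100 per arm, × 2 = 200 assessable; 5 / 0.10 = 50 per arm, × 2 = 100. Section 4.1 recruits 120 to 240, which reproduces as 100 × 1.2 and 200 × 1.2. The plan therefore expects 20 to 40 recruited patients outside the assessable group, against 10 events. It does not say how many would be out for early extubation or early death.

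**2. Direction is open.** Assume 120 randomised per arm, 10 pneumonias in each arm (no effect), all in assessable patients, and 20 placebo patients excluded. With E active patients excluded, the assessable risk ratio is [10/(120 − E)] / [10/100]:

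| E | Risk ratio |
|---|---|
| 10 | 0.91 |
| 20 | 1.00 |
| 30 | 1.11 |
| 40 | 1.25 |

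**3. Illustrative size.** The documents give no daily hazards. Assume pneumonia p = 1.2% and death q = 1.5% per day in both arms, extubation e = 8% on placebo and 13% on active, over 20 days. With S the proportion still on treatment at the start of a day: pneumonia = S·p; death = S(1 − p)q; extubation = S(1 − p)(1 − q)e; the remainder goes to the next day. Non-assessable = deaths on Days 1–2 plus extubations on Days 1–4. Assessable risk = total pneumonia / (1 − non-assessable).

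| Placebo vs active | Extubation from Day 1 | None before Day 4 |
|---|---|---|
| All-treated risk | 10.2% vs 7.5% | 12.5% vs 10.3% |
| All-treated risk ratio | 0.74 | 0.83 |
| Non-assessable | 29% vs 43% | 10% vs 15% |
| Assessable risk | 14.5% vs 13.2% | 13.9% vs 12.0% |
| Assessable risk ratio | 0.91 | 0.87 |

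Treating the three hazards as simultaneous instead of sequential changes the risk ratios by at most 0.01. If the day of extubation or death is not counted as a completed treatment day, the assessable ratios become 0.96 and 0.91. If pneumonia on Days 1–2 is also dropped, they become 0.84 and 0.83.

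**4. How much one case matters** (Fisher, two-sided, 100 per arm):

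- 9 vs 1: p = 0.018
- 8 vs 2: p = 0.1005, just above the 0.10 level
- 8 vs 1, that is 8 vs 2 with one early active-arm case left out: p = 0.035

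**5. Effect of the larger denominator alone.** 10 vs 0 gives p = 0.0015 at 100 per arm and 0.0016 at 120 per arm. At the boundary, 8 vs 2 gives 0.098 at 80 per arm and 0.1002 at 96 (80 × 1.2).

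**The case against.** The strongest defence is that this is a double-blind, exploratory Phase IIa study. If the drug changes neither early extubation nor early death, exclusions balance on average and the test keeps its level. Patients are selected for continued ventilation, and Section 1.3 says steady state takes several days, so a large effect in the first four days is not obvious. This stands: bias is possible, not shown, and step 3 shrinks considerably when early extubation is ruled out. But randomisation is there so that the assumption need not be made.

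Four stronger readings are tempting, and the documents do not support them.

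- *The rule deletes the very patients the drug is meant to help.* Section 1.1 hopes to delay pneumonia, "allowing the patient to recover enough to be extubated prior to developing this threatening complication". That describes delay until recovery, not faster extubation, and only extubation before 5 treatment days removes a patient.
- *A patient expected to need 3 days is eligible but unassessable.* Section 4.3 excludes that patient; the mismatch begins at about 4 days.
- *Pneumonia on Day 1–2 is plainly dropped.* The thresholds are tied to death and extubation, and Section 7.2.4 sends such a case to the panel. The text is ambiguous, not exclusionary.
- *The safety set is compromised too*, because it requires patients "having data considered as available and interpretable will be included in the safety analysis". The wording is loose, but no effect on the safety results can be shown.

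**Conclusion.** The point holds and should be corrected before unblinding. The protocol fixes a post-randomisation population for its primary test and defines no all-treated efficacy analysis, so this is not a detail left to a later analysis plan. The certain loss is the protection of randomisation.

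Any bias depends on an unknown treatment effect on early extubation or early death, and its direction cannot be stated. The gap between the all-treated and assessable risk ratios (0.74 vs 0.91, or 0.83 vs 0.87) rests entirely on assumed hazards, including an assumed faster extubation on active drug, and should be read as a range of possibilities. The unclear status of early pneumonia does not rest on those hazards: it follows from the wording of Section 11.2, and a single case can move the result across 0.10.

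**What to change.** In Section 11.2, make the primary efficacy analysis all randomised patients who received at least one dose, analysed as randomised. Count every panel-confirmed *P. aeruginosa* pneumonia from first dose, and use the same count for the 10-case stopping rule. Keep the 3-day, 5-day, no-major-violation set as a secondary per-protocol analysis, and state there how fatal and non-fatal pneumonia before 3 treatment days is handled. In Section 7.1.1 and the synopsis, count all deaths and report cause as a descriptive split.

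The change is one of wording, since Section 7.2.6 already collects pneumonia outcome at Day n+7 whether or not the patient is ventilated. It has two costs. The event rate per analysed patient falls, from about 14% to 10% in the placebo arm of the illustration with extubation from Day 1; that is not slight, although the larger denominator alone barely moves the test. And once a patient is discharged from the study on Day n, the outcome rests on the single Day n+7 contact, so ascertainment is thinner after early extubation; the report should say so.

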2. STUDY OBJECTIVES

Primary objective

- To assess the clinical efficacy of azithromycin 300 mg i.v., used as a quorum-sensing blocker, when compared to placebo for preventing or delaying the occurrence of pneumonia in ventilated patients colonized with *Pseudomonas aeruginosa*

Secondary objectives

- To assess other clinical efficacy variables
- To compare safety profile in target population
- To demonstrate using both *in vivo* and *in vitro* parameters whether azithromycin can be used clinically as a quorum-sensing blocker against *P. aeruginosa*
- To determine whether *P. aeruginosa* can develop resistance to the quorum-sensing blocker effect of azithromycin
- To check whether prolonged treatment with azithromycin may induce resistance to any of 11 antipseudomonal antibiotics
- To verify whether emergence of resistance to other bacteriae may be elicited by assessing rate of infections in both study groups (azithromycin vs. placebo)

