7.2.5 Day n-1 (last day of treatment)

Day n-1 is the last day of treatment and corresponds to:

- Day of extubation due to improvement of patient condition. If a patient has to be re-intubated within 24 hours he will remain in the study and treatment with study drug continued daily until 2nd extubation successful or until Day 20 of treatment whatever happens first
- Exitus day
- Day 20: Treatment with study drug will be stopped even if ventilation will be continued

The required tests will correspond to Day 3 requirements with additional items for discharge unless not feasible:

- Adverse events from previous night
- Local tolerance
- Body temperature (tympanic or rectal) ~7:00
- Blood pressure, heart rate, respiration rate (~8:00)
- Blood gases
- Oxygenation: Pa_{O2}/ FI_{O2}
- Tracheal aspirate #1, collected pre last dose early morning if patient still ventilated for transfer to local laboratory for:
 - Quantification of *P. aeruginosa*
 - Isolation of *P. aeruginosa* strain and storage at -70°C
 - Special Day n-1 assessment for MIC on *P. aeruginosa* strain with 11 antipseudomonal antibiotics (listed under Section 6.2)
- ECG 1-4 hours post drug
- Lung X-ray whenever possible that day
- CPIS (use lung X-ray of same day)
- Clinical endpoints
- APACHE II score
- Tracheal aspirate #2 (for freezing at -70°C and transfer to Geneva laboratory for investigation), collected 6 hours post drug or earlier if extubation planned
- Extubate if applicable, if possible in the afternoon and after collection of tracheal aspirate sample 2, as medically indicated by weaning procedures
- Store ventilation device in sterile pouch at -70 °C, pending shipment to Geneva laboratory

In the case of exitus, the examinations performed on the previous day and on last third day (Day 9, 12, 15 etc.) will be used as Day n-1 values and the respiration device will be recovered and stored as described above.

On **Day n**, no study drug will be administered and the patient will be discharged from the study after physical examination and after collecting blood and urine safety samples. Ventilation will be continued if required.

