8.3 Documentation and Reporting of Adverse Events by Investigator

All adverse events that occur after the subject has signed the informed consent document must be documented on the pages provided in the CRF.

The following approach will be taken for documentation:

- **All non serious adverse events** must be documented on the “Adverse event” page of the CRF (systemic, local if considered clinically significant, biological if considered clinically significant)
- **All serious adverse events** must be documented on the “Serious adverse event form” which will be part of the CRF (basic report and updates). The information will be forwarded to the monitor and to the identified sponsor’s representatives **within 24 hours, or at the latest on the following working**

day, by telephone and by Fax.. The sponsor's representatives will ensure that all legal reporting requirements are met.

Every attempt should be made to describe the adverse event in terms of a diagnosis, and not as a list of symptoms. If appropriate, component symptoms should also be listed below the diagnosis, as comments. Non-specific signs or symptoms may be recorded as a diagnosis. Assessing the relationship to study drug or to study conditions must be performed and rating of intensity provided (definitely not, possibly, probably, not assessable).

The initial serious adverse event report must be as complete as possible, including details of the current illness and (serious) adverse event, and an assessment of the causal relationship between the event and the study medication. Information not available at the time of the initial report (e.g., an end date for the adverse event, laboratory values or investigation results received after the report) must be documented on a follow-up "Serious adverse event" form.

All subjects who have adverse events, whether considered associated with the use of the study medication or to study conditions or not, whether non serious or serious, must be monitored to determine the outcome. The clinical course of the adverse event will be followed up according to accepted standards of medical practice, even after the end of the period of observation, until a satisfactory explanation is found or the investigator considers it medically justifiable to terminate follow-up. Should the adverse event result in death, a full pathologist's report should be supplied, whenever possible.

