Adverse events reported during trial will be listed by treatment. Absolute and relative frequencies of subjects with adverse events (treatment emergent adverse events) will be tabulated by study part, by body system and by dose. Frequencies of subjects with severe and/or related adverse events will be summarized likewise. Local tolerance will be provided by time and by treatment and will be summarized with descriptive statistics for categorized variables by time and treatment.

Laboratory variables

Laboratory findings will be evaluated using a system of predefined changes and clinically significant abnormal values (provided by sponsor), taking into account the investigator's normal ranges. Listings of all variables will be provided by time and by treatment. Descriptive analysis will be presented by time and by treatment.

Physical examination

Listing of all variables will be provided by time and by treatment group. Descriptive analysis for raw data and for changes from baseline will be presented when appropriate.

Blood pressure and heart rate

Listing of all variables will be provided by time and by treatment. Descriptive analysis for raw data and for changes from baseline will be presented by time and by treatment.

ECG

Twelve-lead ECG will be recorded as described in Appendix I, at a speed of 25 mm/sec and calibrated at 10 mm/mV. If a QTc is prolonged (>450 ms or >60 ms vs. baseline), manual checking of QT and calculation of QTc with Bazett's formula will be performed by the investigator for safety purposes. When a patient will have completed treatment, all his ECGs will be transmitted to an experienced cardiologist for manual measurement as per Appendix J. The ECG parameters calculated manually by cardiologist will be used for statistical analysis.

Occurrence of infections

Information on distribution of infections to any bacterial strain will be collected and occurrence compared between study treatment.

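### The safety set adds a judgement about a patient's data to the one-dose rule, which permits dropping dosed patients from the safety denominators; the likely effect is small and the fix is free

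*Protocol*

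**What the plan says.** Section 11.2 of the protocol defines two populations. For the safety analysis a subject must be randomised and must have "at least one dose of medication and having data considered as available and interpretable will be included in the safety analysis". The two parts are joined by 'and', so both must be met. The bullet above it uses the same availability-and-interpretability test to select patients for the clinical and pharmacodynamic analysis, together with minimum treatment durations and the absence of major protocol violations.

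Section 11.3, under safety parameters, states what the set feeds. "Absolute and relative frequencies of subjects with adverse events (treatment emergent adverse events) will be tabulated", and "Frequencies of subjects with severe and/or related adverse events will be summarized likewise". Laboratory values, physical examination, blood pressure, heart rate and ECG follow as listings and descriptive summaries. The last item under that heading is occurrence of infections, which is to be compared between the treatments. Section 7.1.4 also counts emergence of non-Pseudomonas infections as safety data. For individual events, section 11.3 says: "Adverse events reported during trial will be listed by treatment".

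Section 2 gives the purpose as a secondary objective: "To compare safety profile in target population".

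**The concern.** Membership of a safety set should follow from exposure alone. Here a dosed patient also has to pass a judgement about the data, made after randomisation. The protocol gives no criterion for that judgement. 'Interpretable' also asks for more than 'available': a patient can have a full record and still be judged hard to interpret. In intensive care, where section 8.1.2 expects several deaths and serious events, complicated courses will be common.

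If the judgement is related to a patient's course, the tabulated rates can move in either direction, and not necessarily by the same amount in both arms. The listings keep the events, but they do not restore a denominator. What is at stake is how exactly the safety comparison is reported. The primary test, its significance level and the sample size are not affected.

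**Working it through.** The protocol gives no figure to reproduce, so the check has a textual part and an illustration.

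**Text**

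1. Is the data clause a condition for entry? Yes. Section 11.2 joins it to the dose requirement with 'and'.
2. Is it plausibly a rule for selecting patients? Yes. The preceding bullet uses the same phrase to choose patients for the efficacy set.
3. Does another section restore all dosed patients? No. Section 11.3 names no separate denominator for AE frequencies. Section 8.3 secures documentation and section 11.3 secures listing, but neither defines who is counted.
4. Does the clause require any exclusion? No. It names no type of dosed patient who must be left out.

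**Illustration**

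Inputs:
- Recruitment of 120 to 240 patients (section 4.1) in equal groups (section 5.3), so n = 120/2 = 60 to 240/2 = 120 per arm, taking all as dosed.
- Assumed, not in the protocol: a true AE rate of 10%, so e = 6 of 60 or 12 of 120, and m = 1 to 3 patients dropped in an arm.

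*Patients without an AE dropped*, rate = e/(n − m):

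| m | n = 120 | n = 60 |
|---|---|---|
| 1 | 12/119 = 10.08% (+0.08) | 6/59 = 10.17% (+0.17) |
| 3 | 12/117 = 10.26% (+0.26) | 6/57 = 10.53% (+0.53) |

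*Patients with an AE dropped*, rate = (e − m)/(n − m):

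| m | n = 120 | n = 60 |
|---|---|---|
| 1 | 11/119 = 9.24% (−0.76) | 5/59 = 8.47% (−1.53) |
| 3 | 9/117 = 7.69% (−2.31) | 3/57 = 5.26% (−4.74) |

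The first table fits the wording better, because a patient with a recorded AE has safety data. If such removals occurred in one arm only and the true rates were equal, the spurious difference would be the figure in brackets. With m = 0 the shift is zero.

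The shift in the first table grows with the assumed rate. At 30%, dropping 3 patients without an AE gives 36/117 = 30.8% or 18/57 = 31.6%, a rise of 0.8 or 1.6 points.

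**The case against.** The best defence is that the clause means only that a patient has some usable safety data, and that almost every dosed patient will. Study staff give the doses in an intensive care unit, and AEs and vital signs are recorded daily. Section 8.3 is firm: "All adverse events that occur after the subject has signed the informed consent document must be documented". For a death, section 7.2.5 supplies substitute values: "In the case of exitus, the examinations performed on the previous day and on last third day" serve as those of Day n-1. Section 9.1 asks, as far as possible, for final-day examinations in dosed patients who do not complete, and section 7.2.6 collects AEs again at Day n+7. The study is double blind, and section 11.3 promises a detailed statistical plan before decoding, which could give the phrase this mild meaning. Safety output is mainly descriptive.

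Most of this stands, and it is why the expected effect is small. Blinding and the later plan also make selection by knowledge of the arm less likely. Two things remain. The safeguards secure that data are available, not that someone will judge them interpretable. And blinding does not prevent exclusions that depend on a patient's course. The condition is already written into the protocol, so it is a stated rule that can be improved and not a detail left for the analysis plan.

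A reader might infer that AE rates will be understated by several points. The documents do not support that: it requires removing patients whose AEs were recorded, which is the less fitting reading of the clause, and nothing in the protocol calls for it.

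**Conclusion.** The point holds as a defect of wording with low weight. Section 11.2 permits discretionary exclusion of dosed patients from the safety analysis as a whole, including the AE frequencies, the severe and/or related AEs and the infection comparison under safety parameters. For laboratory, ECG and vital-sign summaries the clause changes little, since a patient without a value is absent from them anyway. For infections the reach is less certain, because section 7.1.1 also lists infections with other strains under clinical efficacy and the protocol does not say which set applies.

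The likely size is zero to about 0.5 percentage points. This rests on an assumed AE rate of 10%, 60 to 120 patients per arm and at most 3 dropped per arm, none with an AE; a higher rate scales it up as shown. The number actually dropped cannot be derived and may be none.

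A reader might also infer that the clause could hide deaths. The documents do not support this. Section 7.1.1 makes death a clinical efficacy variable, "Occurrence of death (excluded if death within 3 days and not elicited by" the study pathogen, with its own exclusion rule, and section 11.3 names no separate table of deaths or serious AEs. That early-death rule belongs to the efficacy side and is no part of this point.

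**What to change.** In section 11.2, define the safety set as all randomised subjects who received at least one dose of study medication, and delete the clause that begins with 'and having data'. How missing laboratory, ECG or vital-sign values are handled can be left to the statistical analysis plan.

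The cost is one deleted clause. No new data, procedures or patients are needed, and nothing changes for the primary analysis. Tabulated rates might differ slightly, in either direction, from those under the present wording. This is a low-priority improvement.
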